MDI	Metered Dose Inhaler
PI	Principal Investigator
SAE	serious adverse experience

PROTOCOL SYNOPSIS

TITLE	Flunisolide HFA in Children with Small Airway Disease
FUNDING AGENCY	MEDA Pharmaceuticals
PRINCIPAL INVESTIGATORS	[name] University of Louisville Louisville, KY [name] University of Louisville Louisville, KY
PRINCIPAL INVESTIGATOR SPONSOR	MEDA Pharmaceuticals
DATA COORDINATING CENTER	University of Louisville Physicians – Pediatric Pulmonology (Academic Office)
NUMBER OF SITES	One
STUDY DESIGN	Prospective, randomized, parallel, open label study
OBJECTIVE	To assess whether there is a dose-related difference with flunisolide HFA in pediatric patients with small airway obstruction based on pulmonary function parameters specifically designed to measure changes in small airway function.
NUMBER OF SUBJECTS	50

SUBJECT ELIGIBILITY CRITERIA	
Inclusion Criteria:
 
1. Diagnosis of asthma by pediatrician or asthma specialist2. Informed consent by parent or legal guardian3. 6 years to 21 years of age at Screening Visit4. Ability to comply with medication use, study visits and study procedures as judged by the site investigator5. $\text{FEF}_{25-75\%} < 65\%$ of predicted as a marker for small airway disease 
Exclusion Criteria:
 
1. Acute wheezing at Screening visit or at Baseline visit2. Acute intercurrent respiratory infection, defined as an increase in cough, wheezing, or respiratory rate with onset in 1 week preceding Screening visit or 3 weeks preceding Baseline visit3. Oxygen saturation $< 94\%$ at Screening visit or at Baseline visit4. Clinically significant upper airway obstruction as determined by the Site Investigator (e.g. severe laryngomalacia, markedly enlarged tonsils, significant snoring, diagnosed obstructive sleep apnea)5. Severe gastroesophageal reflux, defined as persistent frequent emesis despite anti-reflux therapy6. Physical findings that would compromise the safety of the subject or the quality of the study data as determined by site investigator7. ICS use within 7 days of Baseline visit, systemic steroid use within 30 days of Baseline visit8. CF, ILD, history of severe BPD or other underlying significant respiratory disease apart from asthma9. Patients who are pregnant may not enroll in this study
TEST DRUG, DOSE AND MODE OF ADMINISTRATION	Flunisolide HFA (Aerospan™, MEDA Pharmaceuticals, Somerset, NJ) 1 or 2 inhalations administered via MDI twice daily for 6 weeks.

DURATION OF SUBJECT PARTICIPATION AND DURATION OF STUDY	Study visits will occur at screening, baseline, and 6 weeks (± 1 week). Total duration of subject participation will be up to 8 weeks. As enrollment will occur over approximately 12 months, total duration of the study is expected to be up to 14 months (12 months enrollment plus about 2 months for the last subjects to complete treatment).
Screening, enrollment, randomization and treatment	
Screening: At the Screening visit, a focused, standardized history and physical exam will be conducted by one of the physicians on the research team. Patients will also undergo pre and post bronchodilator spirometry. Spirometry values prior to the administration of bronchodilator will be used to assess patient's enrollment status.
 
Enrollment and Randomization: At the Baseline visit, patients will undergo a repeat focused, standardized history and physical exam. Spirometry and IOS will both be undertaken pre and post bronchodilator (in this order: IOS, spirometry, bronchodilator, IOS, spirometry).
 
Treatment: Subjects will receive treatments twice per day for 6 ± 3 days.

CONCOMITANT MEDICATIONS	
Allowed: All standard therapies
 
Prohibited: Other forms of ICS, LABAs

Efficacy Evaluations	Physiologic effects (change in lung function between baseline and end of treatment) and Clinical Effects (number of asthma exacerbations, asthma control scores) will be compared between subjects randomized to flunisolide HFA 1 inhalation BID and to flunisolide HFA 2 inhalations BID.
Primary endpoint	The average change in FEV1, FEF25-75% , R5, R5-R20, AX, Fres and X5 measured by spirometry and IOS during from baseline to end of treatment (6 ± 3 days) between subjects randomized to flunisolide HFA 1 inhalation BID and to flunisolide HFA 2 inhalations BID.
SECONDARY	The number of protocol-defined asthma exacerbations requiring

ENDPOINTS	treatment with oral steroids between subjects randomized to flunisolide HFA 1 inhalation BID and to flunisolide HFA 2 inhalations BID.
SAFETY EVALUATIONS	Rates of adverse events, withdrawal, adherence to treatment, rate of asthma exacerbations will be monitored.
SAFETY MONITORING	As this is an FDA approved drug being used in approved populations at approved doses, the elements listed under "safety evaluations" as above will be tracked by the PIs but no formal data safety review board will be in place.
STATISTICS Primary Analysis Plan	The primary aim is to compare the average change in spirometric values (FEV1 and FEF _{25-75%}) and IOS values (R5, R5-R20, AX, Fres) from baseline to Week 6 from participants randomized flunisolide HFA 1 inhalation BID and to flunisolide HFA 2 inhalations BID. The change in scores from baseline to six-week follow-up will initially be compared using paired t-tests and Chi-squared tests for trend. Repeated measurements will be analyzed using generalized linear mixed-effects regression modeling (GLMM) techniques. For continuous outcomes (e.g., FEV1, FEF _{25-75%} , Fres, X5, AX, R5-R20.) the identity link function and normal distribution will be used. For count data (e.g., use of Beta-agonists, episodes of coughing, episodes of wheezing, etc.) the log link function and the Poisson distribution will be used. If we dichotomize outcomes (e.g., a Beta-agonist was used, coughing occurred, etc.) the logit link function and Bernoulli distribution will be used. Statistical analyses will be performed using SAS® Version 9.3 (SAS Institute Inc., Cary, NC).
Rationale for Number of Subjects	Based on our preliminary studies, we anticipate that 10% of all potential participants will not be eligible and/or willing to participant; and that 10% of the eligible/willing participants will be lost to follow-up. Therefore, we will recruit a total of n=50 individuals for the current study. This is a feasible sample size for the research team to recruit and enroll in the current study. Power calculations were based

on the anticipated total sample size (n=40) that will be available for complete analysis.

We will develop separate mixed-effects general linear models for each of the continuous outcomes. From the anticipated sample size (n=40) the study has 86% power to detect a 10% main effect of each treatment for each outcome, our anticipated effect size given preliminary studies. When using count data the study has 94% power to detect a 10% decrease in the rate of outcomes (coughing, wheezing, etc.), our anticipated change in the rate. Using the dichotomized version of some outcomes, this study has 80% power to detect an odds ratio of 1.32 with a two sided $\alpha=0.05$ (n=40). Therefore, we have more than sufficient numbers of participants in each comparison group.

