1 BACKGROUND

Flunisolide HFA is an inhaled corticosteroid that is a reformulated version of the older CFC preparation. The CFC formulation was approved in 1981 and had been in use as an asthma controller since with good results.¹ The HFA formulation, which is in solution as opposed to suspension, has superior lung deposition when compared to its CFC counterpart (68% versus 20%).¹ Studies have demonstrated flunisolide HFA's effectiveness with regards to controlling airway inflammation and improving lung function^{2,3} while maintaining an excellent side effect profile, including no measurable effect on growth over one year.⁴ These attributes make it ideal for use in pediatric patients in whom growth suppression is a common concern. In addition, the current device used for delivery has a built-in spacer to ensure optimal lung deposition.

It is known that flunisolide HFA is uniformly distributed throughout all airways, with deposition approaching 68% and less drug being deposited in the oral cavity than larger molecule inhaled corticosteroids. Fluticasone, for example, has a larger particle size and results in about 20% lung deposition, mainly in the central airways. Despite this, there is little data that specifically examines the effect of flunisolide HFA on small airway parameters in children with asthma. We propose a randomized parallel study between flunisolide HFA 80 mcg twice a day and 160 mcg twice a day to determine the effect of each dose on spirometry and impulse oscillometry (IOS) parameters.

Based on the small molecule size and even lung deposition, we hypothesize that we will see a dose dependent significant improvement in small airway parameters (FEF 25-75%, AX, Fres, X5, R20-R5) with flunisolide. Secondary outcome measures will include clinical effects such as frequency of coughing and wheezing, number of short acting beta agonists used, oral steroid doses required, emergency department visits, and hospitalizations. If the results support our hypothesis this will address an important problem in the field and shift current clinical practice paradigms by a refinement in interventions. It may also provide the foundation for future studies to directly compare flunisolide to other coarse molecules inhaled corticosteroids.

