1.7 Rational for lung function as primary endpoint

We are using change in lung function parameters (FEV1, FEF25-75% from spirometry, R5, R5-R20, AX, Fres from IOS) as a means of assessing response as this provides an objective means of demonstrating improvement in both large and small airways. FEV1 is a well-established parameter in assessing lung function and overall asthma control while FEF25-75% is recognized for its ability to determine small airway obstruction.¹⁴ IOS is an emerging pulmonary function test using sound waves reflected down the pulmonary airway and back designed to assess airway parameters in an effort independent fashion. While the details of its full clinical use is beyond the scope of this article, there are several recent review articles that provide a detailed discussion of the utility of IOS.^{15,16} One key attribute of IOS is that data suggests it may be more sensitive in detecting changes in the small airways than traditional spirometry.¹⁷⁻²⁰ Lung function is routinely used in practice as a means of assessing control and thus these findings will be readily applicable to the clinician. While the pivotal trials of Aerospan looked only at FEV1 changes (a measure of large airway dysfunction), our study proposes to look into small airway function as well.

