4.2 Primary Efficacy Endpoint

The average change in FEV1 and FEF25-75% measured by spirometry at baseline visit and again 6 weeks later as well the average change in R5, Area of Reactance (AX), and X5 between the two visits as measured by IOS.

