15.1 Analysis of Physiologic Effects (Lung Function)

The primary goal of the current study is to determine the effects of Aerospan on lung function in children with small airway obstruction. Participants recruited into this randomized parallel group study will be randomly assigned to either receive (1) 80 mcg of Aerospan twice a day or (2) 160 mcg of Aerospan twice a day, during the six-week study period. Outcomes will be measured at baseline and at six-week follow-up as described above.

First we will start with straightforward tests for differences among the two groups to test if our randomization scheme was successful. Analysis of Variance (ANOVA) techniques will be used to test for difference among continuous variables, while Kruskal-Wallis, Fischer's Exact Tests and Wilcoxon methods will be used to test for differences among categorical variables.

The primary endpoint will be changes in outcomes, over time, from baseline to six-week follow-up. The change in scores from baseline to six-week follow-up will initially be compared using paired t-tests and Chi-squared tests for trend. Repeated measurements will be analyzed using generalized linear mixed-effects regression modeling (GLMM) techniques. For continuous outcomes (e.g., FEV1, FEF 25-75%, Fres, X5, AX, R5-R20.) the identity link function and normal distribution will be used. For count data (e.g., use of Beta-agonists, episodes of

coughing, episodes of wheezing, etc.) the log link function and the Poisson distribution will be used. If we dichotomize outcomes (e.g., a Beta-agonist was used, coughing occurred, etc.) the logit link function and Bernoulli distribution will be used. Statistical analyses will be performed using SAS® Version 9.3 (SAS Institute Inc., Cary, NC).

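### The primary endpoint is listed as seven, six or five lung-function variables in different places, and the text fixes no lead variable, bronchodilator state, between-dose contrast, success rule or multiplicity rule

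*Combined protocol and SAP*

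**What the plan says.** Four places name the primary variables.

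- **Synopsis, Primary endpoint:** FEV1, FEF25-75 and "R5, R5-R20, AX, Fres and X5 measured by spirometry and IOS", compared between the two doses.
- **Synopsis, Primary Analysis Plan (aim):** FEV1, FEF25-75 and "IOS values (R5, R5-R20, AX, Fres) from baseline to Week 6", again between doses.
- **Section 1.7:** "FEV1, FEF25-75% from spirometry, R5, R5-R20, AX, Fres from IOS".
- **Section 4.2:** FEV1 and FEF25-75, "as well the average change in R5, Area of Reactance (AX), and X5 between the two visits as measured by IOS".

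Section 15.1 names no variables in its definition: "The primary endpoint will be changes in outcomes, over time, from baseline to six-week follow-up". It says that the changes "will initially be compared using paired t-tests and Chi-squared tests for trend", and then moves to a generalized linear mixed model. The Synopsis and section 15.2 plan a separate model for each continuous outcome and give 86% power for each.

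Two further lists are not labelled as the primary endpoint. Section 15.1 and the Synopsis illustrate the choice of link function: "For continuous outcomes (e.g., FEV1, FEF 25-75%, Fres, X5, AX, R5-R20". The Background hypothesis expects a dose-dependent "improvement in small airway parameters (FEF 25-75%, AX, Fres, X5, R20-R5) with flunisolide".

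Sections 9.2 and 9.3 collect IOS and spirometry before and after bronchodilator at both visits. Pre-bronchodilator values are specified only for eligibility (Synopsis, Screening; section 4.1). Section 15 promises a detailed SAP before the analysis.

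**The concern.** A primary endpoint should let a reader say in advance which result decides the question. Here the variable, the bronchodilator state and the test are all open. An SAP written later would first have to choose between conflicting definitions. Section 15 requires it only before analysis, not before outcomes are seen, and the trial is open label (section 4.1).

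The choice could settle the conclusion. Section 1.6 reports that in children aged 6 to 11 the 160 mcg twice-daily dose added nothing over 80 mcg on percent-predicted FEV1, whereas the Background expects a dose response in small-airway measures. Different variables may therefore give different answers. If one favourable variable out of several were reported as the dose effect, readers could not tell a prespecified finding from the best of the set.

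**Working it through.** **1. The lists side by side**

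| Variable | Synopsis, endpoint | Synopsis, aim | 1.7 | 4.2 |
|---|---|---|---|---|
| FEV1 | yes | yes | yes | yes |
| FEF25-75 | yes | yes | yes | yes |
| R5 | yes | yes | yes | yes |
| AX | yes | yes | yes | yes |
| R5-R20 | yes | yes | yes | no |
| Fres | yes | yes | yes | no |
| X5 | yes | no | no | yes |
| Count | 7 | 6 | 6 | 5 |

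Four variables are common to all four lists. R5-R20, Fres and X5 are each missing from at least one. All three are in the Background hypothesis (reading its R20-R5 as R5-R20).

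**2. The test.** A paired t-test on baseline and six-week values asks whether a child changed. In a parallel-group trial it does not ask whether the doses differ. The mixed model could answer that through a dose-by-visit term, but no model terms are given, and neither method is called primary.

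**3. The plan's own figures.** Analysable number: 50 × 0.9 × 0.9 = 40.5, so 40 is reproduced. The 86% power cannot be reproduced, because no SD is given and the stated effect, 10% for each treatment, need not be a between-dose difference. Solving back from 86% at two-sided 0.05 (t-based):

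| Reading of the 86% | Standardised effect | SD if the effect is 10 |
|---|---|---|
| Two arms of 20 | 0.99 | 10/0.987 = 10.1 |
| Paired, one arm of 20 | 0.72 | 10/0.717 = 13.9 |
| Paired, all 40 | 0.49 | 10/0.493 = 20.3 |

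For a between-dose difference of 10 with 20 per arm, power is 87% at SD 10, 54% at SD 15 and 34% at SD 20.

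**4. False positives if any one variable could win.** Three assumptions are not in the documents: that success rule, two-sided 0.05 for each variable (the protocol states 0.05 only beside the odds-ratio power), and equal correlations ρ between the test statistics. With independence the chance is 1 − 0.95^k. With correlation it is P(max|Z| > 1.96) for k equicorrelated normals, by simulation with 1,000,000 draws.

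| k | ρ = 0 | ρ = 0.5 | ρ = 0.9 |
|---|---|---|---|
| 5 | 23% | 18% | 10% |
| 6 | 26% | 21% | 11% |
| 7 | 30% | 23% | 11% |

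The independence column is an implausible upper bound, since R5-R20 contains R5. For a false claim in favour of the higher dose, the range over ρ = 0.9 to 0.5 is 5-11%, against a nominal 2.5%. Two-sample t-tests with 20 per arm agree within 0.6 percentage points. If every variable had to succeed, there would be no inflation.

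**The case against.** It can fairly be said that an SAP covering all analyses is promised, that Table 1 and Appendix 1 are not in the supplied text, and that small trials often report a panel of lung-function measures. This limits every statement of absence to the supplied text. It does not remove the conflict between current sections, which an SAP would inherit.

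Four stronger readings are tempting, and the documents do not support them.

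- **Only FEV1, FEF25-75 and AX are common to every list.** R5 drops out only if the list of continuous outcomes in section 15.1 is counted. That list is introduced as examples and illustrates a link function. R5 is in all four primary lists.
- **No comparison of doses is planned.** The Synopsis declares one twice, and a mixed model is named. What is missing is the contrast and a statement of which analysis is primary.
- **FEV1 does not belong in a small-airway trial.** Section 1.7 explains that the set is meant to show response in large and small airways, and section 3.1 states the objective as lung function generally.
- **The plan has a 10-23% error rate.** The plan states no success rule, so it has no defined error rate.

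**Conclusion.** The point holds, and it should be fixed before outcome data are examined. It rests on the text alone: four primary lists with seven, six, six and five variables, a first-named test that does not address the declared comparison, two bronchodilator states with neither chosen, and no rule for deciding success. Followed as written, the plan cannot yield one defined answer.

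The 10-23% range shows what is at stake under the assumptions in step 4 of the working. It moves with the correlation and vanishes under an all-must-succeed rule. The inconsistency stands without it.

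**What to change.** Before any outcome data are examined, state one identical primary endpoint in the Synopsis (endpoint row and analysis plan) and in sections 1.7, 4.2 and 15.1. Align the Background hypothesis with it and carry it into the promised SAP. It should give:

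1. One named variable in a stated unit. The choice is the sponsor's; FEF25-75 as percent predicted (the eligibility marker) or one IOS variable would fit the documents.
2. One bronchodilator state.
3. One test: the between-dose contrast in change from baseline to the six-week visit, from the planned identity-link mixed model, at two-sided 0.05. The paired t-tests become descriptive.
4. Error control for the other lung-function variables. One option is Holm over the remaining six (smallest p against 0.05/6 = 0.0083), only after a significant primary. Another is one fixed list of seven with Holm across it (0.05/7 = 0.0071). Other schemes are acceptable if fixed in advance.
5. Under either option, power in the Synopsis and section 15.2 restated for that contrast with the assumed SD.

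The differing statements of visit timing are a separate matter and must also be reconciled.

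**Cost.** Wording only; this point proposes no change to enrolment or measurements. The price is that the other variables can be claimed only through the gate or at an adjusted level. How much is lost depends on how the 86% was derived. Suppose all seven between-dose effects are real, of equal standardised size, with 20 per arm and correlations of 0.5 to 0.9:

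- At 0.99 (86% from a two-arm test), each gated variable is claimed about 69-71% of the time, and each variable under Holm across seven about 70-73%, against 86% if tested alone.
- At 0.72, power is about 60% for the primary and roughly a third for each gated variable.
- At 0.49, it is about 33% and roughly 10-15%.

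The restated power section should show such a range.

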1 BACKGROUND

Flunisolide HFA is an inhaled corticosteroid that is a reformulated version of the older CFC preparation. The CFC formulation was approved in 1981 and had been in use as an asthma controller since with good results.¹ The HFA formulation, which is in solution as opposed to suspension, has superior lung deposition when compared to its CFC counterpart (68% versus 20%).¹ Studies have demonstrated flunisolide HFA's effectiveness with regards to controlling airway inflammation and improving lung function^{2,3} while maintaining an excellent side effect profile, including no measurable effect on growth over one year.⁴ These attributes make it ideal for use in pediatric patients in whom growth suppression is a common concern. In addition, the current device used for delivery has a built-in spacer to ensure optimal lung deposition.

It is known that flunisolide HFA is uniformly distributed throughout all airways, with deposition approaching 68% and less drug being deposited in the oral cavity than larger molecule inhaled corticosteroids. Fluticasone, for example, has a larger particle size and results in about 20% lung deposition, mainly in the central airways. Despite this, there is little data that specifically examines the effect of flunisolide HFA on small airway parameters in children with asthma. We propose a randomized parallel study between flunisolide HFA 80 mcg twice a day and 160 mcg twice a day to determine the effect of each dose on spirometry and impulse oscillometry (IOS) parameters.

Based on the small molecule size and even lung deposition, we hypothesize that we will see a dose dependent significant improvement in small airway parameters (FEF 25-75%, AX, Fres, X5, R20-R5) with flunisolide. Secondary outcome measures will include clinical effects such as frequency of coughing and wheezing, number of short acting beta agonists used, oral steroid doses required, emergency department visits, and hospitalizations. If the results support our hypothesis this will address an important problem in the field and shift current clinical practice paradigms by a refinement in interventions. It may also provide the foundation for future studies to directly compare flunisolide to other coarse molecules inhaled corticosteroids.

